15.2.2 SECONDARY ENDPOINT ANALYSIS

Day 84; Alerts from Path Active will be analysed to assess a base level of sensitivity and specificity.

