4.0 STUDY FLOW CHART

5.0 INTRODUCTION

5.1 BACKGROUND

More than 4.9M people have been diagnosed with diabetes (DM) in the UK, and up to 25% (1.2M) will develop a Diabetic Foot Ulcer (DFU) in their lifetimes. 15-20% of DFUs lead to amputations which are followed by significantly increased mortality. The cost to taxpayers is enormous (Kerr 2019), consuming 1% of NHS budget annually.

The current method of providing periodic foot checks is inadequate, with the chance of recurrence of an ulcer being 40% in the first year, rising to almost 100% over 10 years (Armstrong 2017). Individuals at high risk of DFU go to clinic to have their feet checked at least once a month. This can be highly disruptive to their everyday lives. Furthermore, there is considerable environmental cost of patient travel and if a DFU occurs single-use consumables for treatment such as dressings, bandages, scalpels, blood tests, cultures for microbiology , etc.

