5.2 RATIONALE

Foot ulceration and infection is a major factor leading to morbidity (amputation) and mortality. There are multiple comorbidities which can lead to foot ulceration and infection such as peripheral arterial disease and diabetes. The estimated cost of foot care in England for people with diabetes and foot ulceration alone is £1billion (Kerr 2019) with around 9000 amputations a year (one an hour). Many amputations occur due to ulceration leading to infection.

Path Active is an advanced at-home foot health monitoring system that combines unique patented, sensor-rich insoles and patient-adapted machine learning to prevent DFUs. Path Active does this by accurately mapping and measuring a person's foot pressure and temperature distribution to calculate increasing risk of foot ulceration and allow users to take appropriate actions to reduce their DFU risk. For patients, a highly-visual dedicated UI (User Interface - app & web portal), with embedded behavioural science-led 'nudge methodology', supports and encourages them to offload (rest) their feet to prevent DFU development and liaise remotely with their clinician. These systems have been shown to reduce DFU recurrence with the single modality of pressure measurement (Chatwin 2021; Abbott 2019). Additionally, Path Feel measures temperature change as a precursor to foot disease as well as pressure and reduces the need for frequency of clinic visits by providing at-home monitoring. Alerts are also captured on a clinical dashboard by the patient's clinical team which will alert them to potential foot problems and so they can contact the patient and provide rapid clinical care when required.

From a healthcare professional's perspective, the platform provides a major opportunity to save time and personalise care, focusing on only those patients who need help.

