7.0 TRIAL DESIGN

7.1 METHOD

Study setting

Participants who have been assessed as having a 'high risk' of foot ulceration will be recruited from Community Foot Protection Teams in 4 sites across the UK. Participants will be recruited to the study to a maximum total of 120 (30 at each site) who have completed the study. The number of recruits required is based on a power calculation for the study at the 95% confidence interval.

The study is anticipated to run for 12 months.

Procedure

Potential participants will be approached to participate during routine review by the Community Foot Protection Teams and consented by them for the study. All participants will be screened at pre-assessment by the Community Foot Protection Teams.

Following completion of informed consent the participant will have;

- Medical History
- Arterial Doppler scan

- Test for Neuropathy
- Eligibility confirmation
- EuroQoL Assessment (EQ-5D-5L)
- Patient Questionnaire
- Randomised to 'Path Active Group' or 'Control Group' using computer randomisation.

If the participant is randomised to use the device in the 'Path Active Group';

- Participant Training in device and mobile app use (Appendix 1).

If there is an alert from Path Active app the participant will be asked to reduce walking and rest their feet. If the alert continues and activates the clinical dashboard, patients will be contacted to attend clinic for review.

If the participant is not randomised to use the device in the 'Control Group', they will continue with their regular podiatry clinical reviews with the Community Foot Protection Team who will provide their standard of care.

Day 84 (week 12). At the end of study;

- EuroQoL Assessment (EQ-5D-5L)
- Patient Questionnaire

If the participant is randomised to use the device;

- Device retained by clinical research team.

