8.1 INCLUSION CRITERIA

- Participant able to give informed consent.
- Age >18 at the time of consent.
- Diagnosis of Type 1 or Type 2 Diabetes.
- Both Feet Intact (no ulceration).
- Participant understands and is willing to participate and can comply with the follow-up regime.
- Participant diabetes foot Risk Stratification as 'High Risk' as in Frame (2021) Scotland/England
<https://www.diabetesframe.org/>

- Ability to walk independently for > 100 metres i.e without use of wheelchair, walking stick or personal assistance.
- Participant able and willing to wear suitable footwear.
- Must own a mobile phone and be willing to upload WWP app.

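### Section 15.2.2 plans sensitivity and specificity of the alerts, but alerts change management and equal ulcer ascertainment is not secured, so neither can be estimated without bias

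*Protocol*

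**What the plan says.** Section 15.2.2 (Protocol) commits to an accuracy analysis at Day 84: "Alerts from Path Active will be analysed to assess a base level of sensitivity and specificity". It names no target condition, unit or time window. Section 15.1.2 asks, from a review of the alerts and the responses to them, whether ulceration was prevented.

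Section 7.1 gives the response in two steps: "If there is an alert from Path Active app the participant will be asked to reduce walking and rest their feet", and then "If the alert continues and activates the clinical dashboard, patients will be contacted to attend clinic for review". For the control group it says that "they will continue with their regular podiatry clinical reviews"; it makes no such statement for the device group. Section 5.2 says of the system (there called Path Feel) that it "reduces the need for frequency of clinic visits by providing at-home monitoring". Section 5.1 describes routine practice: "Individuals at high risk of DFU go to clinic to have their feet checked at least once a month".

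In the schedule (Section 10.2) the neuropathy assessment is marked at screening only. The vascular Doppler and the eligibility confirmation are marked at screening and at Visit 3, which takes place on alert or concern. Eligibility includes "Both Feet Intact (no ulceration" (Section 8.1). Week 12 has adverse event review, the questionnaire and EQ-5D-5L, but no foot assessment. Under Sections 12.0.1 and 12.0.2, unrelated events are not reported, apart from death, hospital admission and institutionalisation.

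**The concern.** Sensitivity and specificity describe how well an alert identifies a condition whose occurrence and detection do not depend on the alert. Here both may depend on it.

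1. **The alert changes the outcome.** Resting the feet is meant to prevent the ulcer. If the target is a later ulcer, a correct alert followed by effective rest leaves no ulcer and is scored as a false positive. The better the response works, the worse the device looks.
2. **The alert changes verification.** A continuing alert leads to a clinic review. A device user with no alert and no concern has no scheduled foot assessment after screening. An ulcer missed in such a user is scored as a true negative, which raises apparent sensitivity.

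Followed as written, the analysis would give figures that mix accuracy, the effect of responding, and how ulcers came to light. The data could not separate the three. Controls wear no insole, so there is no group in which alerts occur and are not acted on.

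**Working it through.** The protocol states no sensitivity or specificity, so there is no figure to reproduce. What follows is an illustration.

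**Assumed inputs.** Target: any ulcer by Day 84, per participant. True sensitivity Se = 0.80, true specificity Sp = 0.90. About 60 device users, which is half of the 120 in Section 7.1; 1:1 allocation is not stated. Let e be the share of alerted ulcers averted by the response, and a1 and a0 the shares of the remaining ulcers found in alerted and non-alerted users.

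**Sensitivity.** Apparent Se = Se(1−e)a1 / [Se(1−e)a1 + (1−Se)a0]. Only the ratio r = a0/a1 matters. The result equals Se when r = 1−e, is too low when r is above that, and too high when r is below it. With e = 0.5:

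| r | Calculation | Apparent sensitivity |
|---|---|---|
| 1 | 0.40 / (0.40 + 0.20) | 67% |
| 0.75 | 0.40 / (0.40 + 0.15) | 73% |
| 0.5 | 0.40 / (0.40 + 0.10) | 80% |
| 0.25 | 0.40 / (0.40 + 0.05) | 89% |

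With e = 0.25 it is 0.60/0.80 = 75% at r = 1 and 0.60/0.70 = 86% at r = 0.5.

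**Specificity.** This also needs the 84-day ulcer risk p. The only rate in the protocol is "the chance of recurrence of an ulcer being 40% in the first year" (Section 5.1), a background recurrence figure. At constant hazard, p = 1 − (1 − 0.40)^(84/365) = 11.1%. Assumed annual risks of 20% and 10% give 5.0% and 2.4%.

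Apparent Sp = TN/(TN + FP), where
- TN = (1−p)Sp + p(1−Se)(1−a0)
- FP = (1−p)(1−Sp) + p·Se·e + p·Se(1−e)(1−a1)

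With e = 0.5, p = 0.111 and full ascertainment, TN = 0.889 × 0.9 = 0.800 and FP = 0.089 + 0.044 = 0.133, so apparent Sp = 86%. At the two lower risks it is 88% and 89%. With a1 = a0 = 0.5 the three values are 84%, 87% and 89%.

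**Precision.** With e = 0.5 the expected remaining ulcers in 60 device users are 60 × p × (0.8 × 0.5 + 0.2) = 4.0, 1.8 or 0.9 at the three risks. If 3 of 4 had been preceded by an alert, the exact 95% interval for sensitivity would be 19% to 99%.

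**Verification if the target is a lesion found at review.** The first effect shrinks, because the lesion exists before any averting response is complete. But Section 7.1 requires clinic contact only for alerts that continue, so verification is still partial.

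**The case against.** The strongest reply has four parts.

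*The target is undefined, and a SAP may define it.* A SAP can fix target, unit and window. It cannot undo the response to alerts or add an examination that was not done. A lesion-at-review target weakens the first effect, as shown, but leaves partial verification.

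*Ulcers can be found in other ways.* This is true. Monthly routine checks may continue, Visit 3 can follow a concern as well as an alert, and the clinical team reviews the dashboard daily. Week 12 includes an adverse event review, hospital admissions are reported, Section 12.2 asks for all SAEs to be reported to the Chief Investigator, and consent to record access is sought. A reader might infer that ulcers without an alert go undetected, or that alerts which settle with rest never lead to a visit. The documents support neither: Section 7.1 requires contact for continuing alerts and does not rule it out otherwise, and forms F07 and F08 are not shown. What stands is that equal ascertainment is not secured. The eligibility confirmation at Visit 3 may imply a check for ulcers there, which adds to the imbalance, since Week 12 has no counterpart.

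*The aim is only a base level, and imprecision dominates.* The exploratory wording and the wide interval are real limits on any claim, but neither removes the bias. With complete and equal ascertainment, the illustration still gives 67% rather than 80%.

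*The lack of an ulcer endpoint in Section 15.1.1 is a separate matter.* Agreed; the point does not depend on it.

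**Conclusion.** The concern holds in this form: the design cannot give unbiased sensitivity and specificity for the alerts. Averted ulcers lower apparent sensitivity, and under-detection in non-alerted users raises it. A reader might conclude that the device's accuracy will be overstated, or that it will be understated. Neither can be said, because the sign depends on whether r is above or below 1−e, and the protocol gives neither quantity. The two effects could even cancel.

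The range of 67% to 89% rests entirely on assumed values. The upper end needs ulcers without an alert to be found only a quarter as often as those after one, and should not be read as a forecast. The effect on specificity is smaller, about 1 to 6 points below 90% in the cases shown. This concerns a secondary analysis and is cheap to correct; it should be corrected before the figures are produced.

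**What to change.** **Section 15.2.2.** Replace the accuracy analysis with descriptive reporting:
- alerts per participant-week;
- the proportion escalated to the dashboard;
- the proportion of alert visits with a lesion found;
- ulcers known to have occurred without a preceding alert.

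Add a sentence such as: *These are not estimates of diagnostic accuracy, because alerts change management and verification is incomplete.* If sensitivity or specificity is still shown, give exact intervals and the same caveat.

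**Week 12.** Record the same ulcer check in both arms at the existing visit, if F08 does not already hold it: ulcer present, or healed since Day 0, with date, from the same sources in both arms.

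**Sections 15.1 and 15.2.** Answer whether ulceration was prevented by the randomised comparison of participants with any new ulcer from Day 0 to Day 84, not from device-arm alerts. List it as an endpoint in 15.1 as well as in 15.2, so that the two agree. Common recording matters here too: with equal true risk, finding 60% of ulcers in one arm and 80% in the other gives an apparent risk ratio of 0.6/0.8 = 0.75, and the reverse gives 1.33.

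**Cost.** The sponsor gives up an accuracy claim. Each participant needs a few minutes and a CRF line at Week 12, and lesion presence must be recorded at Visit 3 if F07 does not already hold it. The comparison will be imprecise: 7 of 60 against 4 of 60 is a difference of 5.0 points, with a Newcombe 95% interval of −6.0 to 16.3. Ulcers that healed before Week 12 may still be found unequally. The check does not rescue sensitivity, because the response to alerts remains.

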16.0 DIRECT ACCESS TO SOURCE DATA

The Community Foot Protection Teams will permit trial-related monitoring, audits, REC review, and regulatory inspection(s), providing direct access to source data/documents. Trial participants are informed of this during the informed consent discussion. Participants will be asked to consent to provide access to their medical records.

17.0 ETHICS AND GOVERNANCE REQUIREMENTS

Before Community Foot Protection Teams can enrol patients into the trial, the Chief Investigator must ensure written permission to proceed has been granted by that Trust Research & Development Department (R&D).

The site must conduct the trial in compliance with the protocol as agreed by the Sponsor and, which was given favourable opinion by the Research Ethics Committee (REC) and the Health Research Authority (HRA) where applicable.

The Principle Investigators will be provided (via the Sponsor) with file indexes TMF Index RLFRDDOC0013 and ISF index RFLRDOC0003 for use with SOP019 'Preparation and Maintenance of the Site File – and SOP054 'Preparation and Maintenance of the Trial Master File'. The CI will be responsible for the maintenance of the TMF and may delegate the responsibility of ISF file maintenance to the PI at each participating site.

Within 90 days after the end of the trial, the CI and Sponsor will ensure that the REC is notified that the trial has finished. If the trial is terminated prematurely, those reports will be made within 15 days after the end of the trial.

The CI will supply an End of Study report of the clinical trial to the REC within one year after the end of the trial. The sponsor can provide an End of study Report template RFLRDDOC0005

17.1 DEFINITION OF THE END OF TRIAL

The last patient completing day 84 of the trial.

17.2 ANNUAL PROGRESS REPORTS (APRs)

The Chief Investigator will prepare the APR in accordance with the RFL R&D Office's SOP 056 'Annual Progress Reports'. Following review by the sponsor the report will be sent to the REC. The APR is due for submission annually within 30 days of the anniversary date on which the favourable opinion was given by the Ethics committee, until the trial is declared ended.

17.3 PROTOCOL COMPLIANCE

Any Protocol Deviations, Violations will be documented using the deviation reporting form (Form 10 WWPP2 Protocol Deviation) and processed according to R&D OFFICE SOP 032

The CI will notify the Sponsor immediately of any case where there exists a possible occurrence of a violation of the protocol or a breach of Data protection.

18.0 FINANCE

SBRI Healthcare Selection Panel. Ref SBRIH22P2006

19.0 PEER REVIEW

The documents have been reviewed by the study team, Patient group (PPIE), Sponsor (WWP) and Royal Free Hospital R&D Committee.

20.0 PUBLIC AND PARTICIPANT INVOLVEMENT

Patients have completed questionnaires regarding the study and use of the device. Also a patient group at the Royal Free Hospital have discussed the study and use of the device. Both questionnaires and patient group discussion were favourable of the device and the study.

21.0 INDEMNITY

Normal NHS-indemnity processes apply, as documented in HSG(96)48. This covers negligent harm during the study, and covers NHS staff, medical academic staff with honorary contracts, and those conducting the study. NHS indemnity does not offer no-fault compensation and is unable to agree in advance to pay compensation for non-negligent harm. The sponsoring company will provide indemnity for the management of the study via their liability insurance.

22.0 IP AND DEVELOPMENT POLICY

Intellectual property may be generated from this study and will remain the property of Walk With Path.

23.0 PUBLICATION AND DISSEMINATION POLICY

Publication: "Any activity that discloses, outside of the circle of trial investigators, any final or interim data or results of the Trial, or any details of the Trial methodology that have not been made public by the Sponsor including, for example, presentations at symposia, national or regional professional meetings, publications in journals, theses or dissertations."

All scientific contributors to the Trial have a responsibility to ensure that results of scientific interest arising from Trial are appropriately published and disseminated. The Sponsor has a firm commitment to publish the results of the Trial in a transparent and unbiased manner without consideration for commercial objectives.

To maximise the impact and scientific validity of the Trial, data shall be consolidated over the duration of the trial, reviewed internally among all investigators and not be submitted for publication

prematurely. Lead in any publications arising from the Trial shall lie with the Sponsor in the first instance.

24.0 STATEMENT OF COMPLIANCE

The trial will be conducted in compliance with the protocol, Sponsor's Standard Operating Procedures (SOPs), GCP and the applicable regulatory requirement(s).

The study conduct shall comply with all relevant laws of the EU if directly applicable or of direct effect and all relevant laws and statutes of the UK country in which the study site is located including but not limited to, the Human Rights Act 1998, the Data Protection Act 1998, ICH GCP, the World Medical Association Declaration of Helsinki entitled 'Ethical Principles for Medical Research Involving Human Subjects' (2008 Version), the NHS Research Governance Framework for Health and Social Care (Version 2, April 2005).

This study will be conducted in compliance with the protocol approved by the REC and according to GCP standards. No deviation from the protocol will be implemented without the prior review and approval of the Sponsor and REC

26.0 APPENDICES

Appendix 1

Path Active
Manual_v3.pptx (2).r
